^d Height will only be measured at Visit 1 (Screening); pulse rate, blood pressure, temperature, and body weight will be assessed at every visit. Blood pressure and pulse will be assessed while the participant is supine and standing.

^e HAM-A will be assessed predose at Visits 2, 3, 4, and 6/ET. The HAM-A will be collected only from participants entering the study after the amendment has been IRB approved.

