Like rapastinel, AGN-241751 is a novel NMDAR modulator with partial agonist properties. AGN-241751 has appropriate oral bioavailability and blood brain barrier penetration.

In support of AGN-241751 investigation in human subjects, a series of nonclinical pharmacology studies have been performed. These studies were designed to characterize AGN-241751 in terms of its potential to a) potentiate NMDAR activity; b) strengthen NMDAR-dependent LTP; and c) produce antidepressant-like effects in rat models. Additional safety and tolerability studies were carried out to evaluate AGN-241751's side effect profile, including potential ataxic/sedative and pro-convulsive effects. Besides displaying potent partial agonist activity at NMDAR, AGN-241751 increased NMDAR-dependent synaptic plasticity in rat hippocampus and medial prefrontal cortex in vitro and ex vivo. AGN-241751 was active in several models of depression, and has demonstrated rapid onset of action in rat models of depression without causing CNS side effects. AGN-241751 had no appreciable affinity for over 60 neurotransmitter-receptors and ion channels in a CEREP screen indicating a lack of potential off-target effects. Central nervous system safety and tolerability profile of AGN-241751 was favorable at substantially higher doses relative to its antidepressant doses. Although transient lowering of blood pressure in conscious telemetered dogs was observed in cardiovascular safety studies, there were no findings that preclude its use for further development. In other safety pharmacology studies, AGN-241751 was not associated with any adverse effects. In summary, the safety profile of AGN-241751 supports the proposed clinical doses (0.25 mg up to 25 mg).

Following oral administration, mean oral bioavailability of AGN-241751 in rats and dogs was approximately 100% and 99%, respectively. There was no accumulation after repeat administration and AGN-241751 was rapidly distributed to the target tissue (brain) with T_{max} at 1 hour post dose in rats. Brain to plasma and CSF to plasma AUC ratios were 0.16 and 0.3, respectively.

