9.4.2. Vital Signs

Vital signs (pulse rate, systolic and diastolic blood pressure, oral or tympanic temperature, and body weight) will be assessed at every visit (Part A) and at Screening, Baseline (Day -1), 4 hours postdose at Visit 3 and Visit 10/Discharge (Day 8), Visit 12/ET (Day 14/ET), and Visit 14 (Day 21) (Part B). Height will be assessed at Screening only in both parts of the study.

Blood pressure and radial pulse rate will be measured in the supine position followed by the standing position. The standing measurements should be assessed after a sufficient amount of time (approximately 1 to 3 minutes) has been elapsed to allow the BP to equilibrate in the standing state.

Radial pulse rate should be measured after blood pressure measurements. Blood pressure may be measured manually or by machine, but radial pulse rate should only be measured manually and for a sufficient time to acquire an accurate measurement.

Participants should be instructed not to wear clothing with tight sleeves when they come for clinic visits. Additionally, participants should be kept as calm and undisturbed as possible while blood pressure and pulse rate measurements are taken (eg, there should be no talking while the blood pressure is being measured). The same arm and blood pressure cuff (appropriate to the arm circumference) should be used for all blood pressure measurements.

Whenever possible, the participant's weight will be measured at the same time of day; participants should wear their usual indoor clothing, but take off their jacket and shoes. For each participant, body weight should be determined using the same equipment during the study after ensuring its proper calibration.

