11.3 VITAL SIGNS

Descriptive statistics of actual values and change from baseline for vital signs (systolic and diastolic blood pressures, pulse rate, weight, and temperature) will be presented at each assessment timepoint by treatment.

Vital sign values will be considered PCS if they meet both the observed-value criterion and the change-from-baseline criteria listed in [Table 11-3](#). The number and percentage of participants who have PCS postbaseline vital sign values will be tabulated by treatment group. The percentages will be calculated relative to the number of participants who have available baseline value and at least 1 postbaseline assessment. The numerator will be the total number of participants with available non-PCS baseline value and at least one PCS postbaseline value. A supportive listing of participants with PCS postbaseline values will be provided.

In addition, a tabular display showing all AEs that occurred in participants who had PCS postbaseline vital sign values will be provided.

Table 11-3 Criteria for Potentially Clinically Significant Vital Signs

Parameter	Flag	Criteria ^a	
		Observed Value	Change From Baseline
Supine systolic blood pressure, mm Hg	High	≥ 180	Increase of ≥ 20
	Low	≤ 90	Decrease of ≥ 20
Supine diastolic blood pressure, mm Hg	High	≥ 105	Increase of ≥ 15
	Low	≤ 50	Decrease of ≥ 15
Supine pulse rate, bpm	High	≥ 120	Increase of ≥ 15
	Low	≤ 50	Decrease of ≥ 15
Weight, kg	High	—	Increase of ≥ 7%
	Low	—	Decrease of ≥ 7%
Temperature, °C	High	> 38	—
	Low	< 35	—

a A postbaseline value is considered potentially clinically significant if it meets both the observed-value and the change-from-baseline criteria.

bpm = beats per minute.

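### SAP Table 11-3 screens only supine blood pressure and pulse in Part A, so a fall confined to standing cannot be flagged as potentially clinically significant

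*SAP*

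**What the plan says.** **Collection.** Footnote d of the Part A schedule (Protocol 2.1) requires vital signs at every visit and adds: "Blood pressure and pulse will be assessed while the participant is supine and standing". The SAP's own schedule (Table 4-1) carries the same footnote. Protocol 9.4.2 gives the procedure: "Blood pressure and radial pulse rate will be measured in the supine position followed by the standing position", with the standing reading taken after roughly 1 to 3 minutes.

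**PCS criteria.** Protocol 10.3.5.3 makes a vital sign PCS only if it meets both an observed-value and a change-from-baseline criterion, and leaves the criteria to each part's SAP. It does not restrict them to one posture. SAP 11.3 keeps the two-part rule: "Vital sign values will be considered PCS if they meet both the observed-value criterion and the change-from-baseline criteria listed in" Table 11-3. The table's three BP and pulse parameters are "Supine systolic blood pressure, mm Hg", "Supine diastolic blood pressure, mm Hg" and "Supine pulse rate, bpm". For low systolic BP the observed value must be 90 mm Hg or less and the change must be "Decrease of ≥ 20". For low diastolic BP the limits are 50 or less and a decrease of at least 15.

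**Outputs.** Under SAP 11.3 the by-arm PCS table, the supporting listing and the display of adverse events in PCS participants all depend on Table 11-3. The same section plans descriptive statistics for systolic BP, diastolic BP and pulse without saying which position.

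**Background.** The Protocol Introduction says: "Although transient lowering of blood pressure in conscious telemetered dogs was observed in cardiovascular safety studies", and concludes that nothing found precluded further development.

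**The concern.** A standing reading taken shortly after a supine one is collected to show what happens to BP and pulse on standing. Sites make that paired measurement at every Part A visit, but the rule that picks out individual participants uses only the supine half. The change element does not help, because it is the change from baseline in the same supine parameter and not the difference between the two positions at one visit.

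What is at stake is the individual-level safety screen. By-arm means can hide a few large falls, and PCS criteria exist to catch them. SAP 16.3 says that all postbaseline assessments count towards PCS determination, yet the standing readings have no criterion to meet. BP lowering, although nonclinical, is the one cardiovascular effect the protocol names. Appendix 6 also lets participants stay on stable α1-blockers, diuretics and other antihypertensives, so some may enter already taking BP-lowering drugs.

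**Working it through.** The plan states no figure to reproduce. The check compares what is collected with what is screened, applies the rule to an illustrative participant, and counts the readings involved.

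**1. Collected against screened**

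| Reading | Taken at every Part A visit (Protocol 2.1 footnote d, 9.4.2) | PCS criterion in SAP Table 11-3 |
|---|---|---|
| Supine systolic, diastolic, pulse | Yes | Yes |
| Standing systolic, diastolic, pulse | Yes | None |
| Supine-to-standing change | Derivable at each visit | None |

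Neither document contains a standing or orthostatic criterion or analysis elsewhere.

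**2. The low-systolic rule applied to assumed readings**

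These values are invented for illustration and are not trial data.

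- Supine: 118 at baseline, 112 postbaseline.
- Standing: 114 at baseline, 84 postbaseline.

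The rule requires an observed value ≤ 90 and a decrease from baseline ≥ 20.

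- Supine: 112 > 90, and 118 − 112 = 6 < 20. Neither part is met, so there is no flag.
- Standing, if the same limits applied: 84 ≤ 90, and 114 − 84 = 30 ≥ 20. Both parts would be met, but no row tests this reading.
- Within-visit postural fall: 118 − 114 = 4 at baseline and 112 − 84 = 28 postbaseline. No row tests this either.

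The restriction to supine is all that keeps this participant out of the PCS outputs.

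**3. Scale**

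Visits after Day 1 with vital signs scheduled (Protocol 2.1): Days 2, 8, 9, 15 and 22, which is 5. Planned enrolment is about 100, or 25 in each of 4 arms.

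- All standing sets: 100 × 5 = about 500, an upper limit that assumes no dropout.
- Placebo sets: 25 × 5 = about 125. These are comparator data.
- Day 22 sets: about 100, taken 7 days after dosing ends.
- Active-arm sets on Days 2, 8, 9 and 15: 75 × 4 = about 300.

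**The case against.** The strongest case on the other side is that this is an optional refinement. It has several parts.

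- **Other routes to reporting exist.** The descriptive statistics in SAP 11.3 are not limited to supine. Table and listing specifications are in a separate document (SAP 4.0) that was not supplied. SAP 16.3 says all assessments will be listed. Under Protocol Appendix 4 an abnormal vital sign judged clinically significant is an adverse event, and SAP 11.1 tabulates treatment-emergent events by arm. This stands. A reader might infer that standing values go unreported, or that the trial would claim no BP effect without having tested for one. The documents do not support either inference. The gap is confined to the PCS count, its listing and the linked adverse event display.
- **The pharmacological reason is thin.** The BP lowering was transient and in dogs, nothing describes a postural effect, and the protocol reports acceptable tolerability in healthy volunteers up to 50 mg once or daily for 10 days. This stands too. A reader might infer a known orthostatic risk in people, but the documents report none.
- **The sampling may miss a transient effect.** The drug is described as rapidly cleared with a short half-life. Day 8 follows six days of placebo for everyone, and the Part A schedule does not time vital signs relative to dosing. This limits the expected yield. It is not a reason to leave the readings unscreened.
- **A postural difference does not fit the PCS definition.** Protocol 10.3.5.3 needs an observed value and a change from baseline, and a within-visit difference is neither. This is correct and shapes the fix.
- **No promise is broken.** The protocol leaves the criteria to the SAP, and neither document commits to an orthostatic analysis. This is also correct: the point is a gap in screening and not a contradiction between the documents.

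**Conclusion.** The concern holds in a limited form. Following SAP Table 11-3 as written, a fall in BP seen only on standing cannot be flagged as PCS in Part A, although the readings that would show it are taken at every visit. Up to about 500 scheduled postbaseline standing sets are unscreened, of which about 300 are active-arm sets on Days 2 to 15. Both counts assume full enrolment and attendance.

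The conclusion rests on the published text of the two documents. It does not assume an orthostatic effect in humans or that standing values will be absent from other outputs. Efficacy analyses are unaffected. The Part B SAP, which Protocol 10.3 makes a separate document, was not supplied, so it cannot be said to share the gap. The point merits action because the screen is incomplete for data already collected and the remedy is cheap.

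**What to change.** Before database lock of Part A:

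1. Add rows to SAP Table 11-3 for standing systolic BP, standing diastolic BP and standing pulse, in the observed-value plus change-from-baseline format that Protocol 10.3.5.3 requires.
2. Add a separate summary, outside the PCS definition, of the supine-to-standing change in BP and pulse by arm and visit, with the number of participants exceeding a cut-off. The cut-off is a clinical choice for the sponsor to fix in advance. This summary is needed as well as the new rows, because a large postural fall can leave the standing value above whatever observed-value limit is set.
3. State in SAP 11.3 which position the descriptive statistics use, or that both are summarised. With two readings per visit, change from baseline is otherwise ambiguous.

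The sponsor should also check whether the Part B SAP has the same gap.

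The cost is SAP wording, programming, a few more table rows, and some flags that arise by chance as more criteria are applied. The placebo arm gives the reference rate for those. No new data are collected.

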11.4 ELECTROCARDIOGRAM

Descriptive statistics of actual values and change from baseline for ECG parameters (ie, heart rate, PR interval, QRS interval, QT interval, and QTc interval according to QTcB and QTcF) will be presented at each assessment timepoint by treatment group.

Electrocardiographic parameter values are considered PCS if they meet the higher-limit PCS criteria listed in [Table 11-4](#). The number and percentage of participants with PCS postbaseline values will be tabulated by study treatment group. The percentages will be calculated relative to the number of participants with available non-PCS baseline value and at least one postbaseline assessment. The numerator will be the total number of participants with available non-PCS baseline value and at least one PCS postbaseline ECG value. A supportive listing of participants with PCS postbaseline values will be provided and will include the participant number and the baseline and postbaseline values. A listing of all AEs for participants with PCS ECG values will also be provided.

A shift table from Screening to Day 15 in the investigator's overall interpretation of the ECG will be presented by treatment group for the following categories: normal; abnormal, not clinically significant; abnormal, clinically significant. A tabular display of participants with postbaseline clinically significant ECG abnormalities according to the investigator's overall interpretation will be provided.

The number and percentage of participants with a change from baseline QTc > 30 msec but not exceeding 60 msec and of participants with an increase > 60 msec will be tabulated by treatment group. A supportive listing that includes the participant identification number, all QTc values (including change from baseline values), and all AEs will be provided for all participants who have postbaseline QTc changes > 30 msec.

Table 11-4 Criteria for Potentially Clinically Significant Electrocardiograms

Parameter	Unit	Higher Limit
QRS interval	msec	≥ 150
PR interval	msec	≥ 250
QTcB, QTcF	msec	>500 or Change from baseline (increase of > 60)

QTc = QT interval corrected for heart rate.

QTcB = QT interval corrected for heart rate using the Bazett formula.

QTcF = QT interval corrected for heart rate using the Fridericia formula.

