9.4.3. Electrocardiograms

A 12-lead ECG will be performed at Screening and Visit 6/ET (Part A) and at Visit 1 (Screening), Visit 12/ET (Day 14/ET), and Visit 14 (Day 21) (Part B). ECGs will be performed and electronically transmitted to a central ECG laboratory for analysis according to the instructions provided by the central ECG laboratory. Measurements (in msec) will be recorded for the following parameters: PR interval, QRS duration, and uncorrected QT interval. QTcB (Bazett corrected QT interval) and QTcF (Fridericia corrected QT interval) will be calculated.

The overall interpretation and determination of the clinical relevance of ECG findings using the central ECG interpretation laboratory report will be the responsibility of the investigator and will be recorded in the participant's eCRF.

Throughout the study, the investigator will review the central ECG reports and indicate the clinical significance of all abnormal values, and then sign and file the report in the participant's study file. In case of any abnormal ECG finding, unscheduled ECGs may be conducted at the discretion of the PI.

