10.3.5.4. Electrocardiograms (Part A and Part B)

For Part A and Part B of the study, descriptive statistics of actual values and change from baseline for ECG parameters (ie, heart rate, PR interval, QRS interval, QT interval, and QTc interval) will be presented at each assessment timepoint by treatment.

The number and percentage of participants with PCS postbaseline values will be tabulated by study treatment. The criteria for PCS ECG values will be detailed in the SAP for Part A and the SAP for Part B, respectively. The percentages will be calculated relative to the number of participants with an available non-PCS baseline value and at least one postbaseline assessment. The numerator will be the total number of participants with an available non-PCS baseline value and at least one PCS postbaseline ECG value. A supportive listing of participants with PCS postbaseline values will be provided and will include the participant number and the baseline and postbaseline values. A listing of all AEs for participants with PCS ECG values will also be provided.

A shift table from baseline to the end of study in the investigator's overall interpretation of the ECG will be presented by treatment group for the following categories: normal; abnormal, not clinically significant; abnormal, clinically significant. A tabular display of participants with postbaseline clinically significant ECG abnormalities according to the investigator's overall interpretation will be provided.

The number and percentage of participants with a change from baseline QTc > 30 msec but not exceeding 60 msec and of participants with an increase > 60 msec will be tabulated by treatment group. A supportive listing that includes the participant identification number, all QTc values (including change from baseline values), and all AEs will be provided for all participants who have postbaseline QTc changes > 30 msec.

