16.0 DATA HANDLING CONVENTIONS

16.1 VISIT TIME WINDOWS

Table 16-1 presents the visits assigned for efficacy and safety analyses and the corresponding range of treatment days (window) during which an actual visit may occur.

Table 16-1 Visit Time Windows

Derived Visit	Scheduled Visit Day^a	Window
Baseline	Screening/Day 1 (Visit 2)	last nonmissing assessment before Index1 ^a
Day 2	Day 2 (Visit 3)	Days (Index1 ^a +1, IndexA ^b -1)
Day 8	Day 8 (Visit 4)	IndexA ^b
Day 9	Day 9 (Visit 5)	Days (IndexA ^b +1, IndexA ^b +4)
Day 15	Day 15 (Visit 6)	Days (IndexA ^b +5, day of final double blind visit or ET Visit occurring after IndexA ^b +5)
End of Double-Blind Treatment	The last available post-baseline assessment (unscheduled assessments) during the double-blind treatment period	
Safety Follow-up (Day 22)	Days [Day after final double-blind visit or ET visit occurring after Day 15 (Visit 6)/Early Termination visit]	

a Index1: Day of first double-blind dose

b IndexA: Day of second double-blind dose, if not received, use Index1 + 7 days

If the assessment date (if the assessment date is unavailable, use visit date instead) is on or after the date of the first dose of study treatment, the study day is calculated by assessment date – date of the first dose of study treatment + 1. If the assessment date is before the date of the first dose of study treatment, the study day is calculated by assessment date – date of the first dose of study treatment. Therefore, a negative day indicates a day before the start of the study treatment.

If a participant has 2 or more visits within the same window, the last visit with a nonmissing value will be used for analysis.

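### The SAP's ECG shift table ends at Day 15 instead of the protocol's end of study, undeclared, and so leaves out early-termination ECGs taken before about Day 13

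*SAP*

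**What the plan says.** Protocol 10.3.5.4, which covers Parts A and B together, calls for "A shift table from baseline to the end of study in the" investigator's overall interpretation, by treatment group. The SAP for Part A, section 11.4, plans "A shift table from Screening to Day 15" for the same interpretation, also by treatment group. SAP 17.0, the section for changes from the protocol, says there are none.

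On when ECGs are taken, Protocol 9.4.3 says: "A 12-lead ECG will be performed at Screening and Visit 6/ET (Part A"). The Part A schedule of activities agrees, and its footnote a says that Visit 6/ET is carried out for everyone, including participants who discontinue after randomization.

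On how visits are assigned, SAP 16.1 applies Table 16-1 to both efficacy and safety analyses. The Day 15 row starts at IndexA+5 and runs to the "day of final double blind visit or ET Visit occurring after IndexA"+5. The footnote defines "IndexA: Day of second double-blind dose, if not received, use Index1 + 7 days". A separate row, End of Double-Blind Treatment, is defined as "The last available post-baseline assessment (unscheduled assessments) during the double-blind treatment period". SAP 16.3 gives a matching last-nonmissing rule for safety parameters. The shift-table sentence uses neither.

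**The concern.** Day 15 is the name of a derived visit with its own window. For a participant who leaves early, the ET ECG is the only scheduled postbaseline ECG. If it falls before the Day 15 window opens, a table that ends at Day 15 has no value for that participant, although the ECG was collected and would naturally be the last value under the protocol's wording.

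Participants who stop early, some of them for adverse events, are people a safety table should not lose through a windowing rule. The change is also undeclared, so a reader of the SAP has no sign that the span differs from the protocol's.

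**Working it through.** There is no planned figure to reproduce. The check is to place each possible ET study day in the Table 16-1 windows.

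**Inputs**
- Index1 is Day 1, the day of the first double-blind dose.
- IndexA is nominally Day 8. If the second double-blind dose is not received, it defaults to Index1 + 7 = Day 8.
- The protocol allows visits up to 2 days either side of schedule, so IndexA can range from Day 6 to Day 10.
- Windows: Day 2 is Index1+1 to IndexA−1; Day 8 is IndexA; Day 9 is IndexA+1 to IndexA+4; Day 15 is IndexA+5 onward.

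**Result: derived visit for an ET ECG, by study day**

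| IndexA | to Day 2 | to Day 8 | to Day 9 | to Day 15 |
|---|---|---|---|---|
| Day 6 | Days 2–5 | Day 6 | Days 7–10 | from Day 11 |
| Day 8 (nominal and default) | Days 2–7 | Day 8 | Days 9–12 | from Day 13 |
| Day 10 | Days 2–9 | Day 10 | Days 11–14 | from Day 15 |

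In the nominal case the window opens at 8 + 5 = Day 13. ET ECGs on Days 2 to 12 are left out of a table that ends at Day 15, and those from Day 13 are in it. What decides is the day of the ECG, not whether the participant dropped out.

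**Size.** The documents give no dropout rate. As an assumption only, suppose 4% to 20% leave with an ET ECG before IndexA+5. With about 25 per arm, that is 0.04 × 25 = 1 to 0.20 × 25 = 5 participants per arm, or 4 to 20 of 100 overall. No assumption about how often their ECGs are abnormal can be drawn from the documents.

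**Reach.** The other ECG outputs in SAP 11.4 are not tied to Day 15:
- The by-arm counts of potentially clinically significant values need only one such postbaseline value.
- The by-arm categories for QTc increases above 30 and above 60 msec name no visit.
- The display of participants with clinically significant abnormalities, on the investigator's interpretation, covers any postbaseline ECG.
- SAP 16.3 puts all assessments in the listings.

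What is lost is the by-arm shift itself. For example, a move from normal to abnormal but not clinically significant in someone who left on Day 10 would appear in the listings but in no by-arm summary of the interpretation.

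**The case against.** The strongest reply is that Day 15 here is simply the label of the Visit 6/ET column. In both schedules of activities that column carries study day 15, and Part A has ECGs only in the Screening and 6/ET columns. On that reading the sentence names the two ECG columns and every ET ECG is included. This is plausible, but the SAP does not say so, and Table 16-1 states that it governs safety analyses. A programmer following it would leave the early ECGs out.

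A second reply is that Protocol 5.3 defines the end of study for the study as a whole, not as a participant-level visit, and Part A has no ECG at Day 22. Naming the last scheduled ECG may therefore be a reasonable specification for Part A. That stands in part: it is a fair inference, not an explicit statement, that the protocol's table would take an early ET ECG as the final value. It does not explain why SAP 17.0 is silent.

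Third, replacing baseline with Screening changes little. Screening is the only scheduled predose ECG in Part A, so the two differ only if an unscheduled predose ECG was taken. This objection stands.

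**Conclusion.** Wrong as written, and minor. The span differs from the protocol's, the difference is not declared, and on the literal windows an ET ECG before IndexA+5 (nominally on or before Day 12) is left out of the only by-arm shift summary of the investigator's overall interpretation.

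Two stronger readings are tempting and are not supported. A reader might infer that the table covers completers only; it does not, because the Day 15 row expressly admits ET visits after IndexA+5. A reader might also infer that an arm difference in clinically significant ECGs could be hidden; the SAP separately displays every participant with a clinically significant postbaseline abnormality, and the counts and QTc categories use any postbaseline ECG.

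The conclusion rests on two assumptions: that Day 15 means the derived visit in Table 16-1, and that the ET visit includes an ECG, as the Visit 6/ET column shows. On the second, Protocol 8.1 defines the final assessment at early termination by the Follow-Up Visit evaluations, which contain no ECG in Part A. Those passages conflict and must be reconciled. The number of participants affected cannot be sized from the documents.

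**What to change.** In SAP 11.4, change the span of the shift table to: *from baseline to End of Double-Blind Treatment (Table 16-1; last available postbaseline ECG, including the Visit 6/ET ECG whatever its study day)*. The closing words are needed because SAP 4.0 ends the double-blind period with the last dosing day, and an ET visit may come after the last dose.

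If Day 15 is intended, say so in SAP 17.0 with the reason, and state how earlier ET ECGs are handled. A row for the worst postbaseline interpretation would be a useful option, but neither document calls for it.

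The cost is one sentence in the SAP and the use of a derived visit that already exists. No new data are needed and no trial procedure changes.
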